9 STATISTICAL CONSIDERATIONS

9.1 Study Design and Sample Size

This is a multi-center, multi-national, prospective, and single arm study. A total of 60 patients will be enrolled in the study. This sample size is adequate to evaluate the safety and performance of the PASCAL System. Recent studies for CE marking of novel mitral repair technologies (listed in Table 8 below) have used sample size of 30 to 35 patients. A sample size of 30 patients is therefore appropriate to reasonably assess the safety profile and technical performance of the PASCAL device.

The analysis population will consist of 60 patients. No site will be allowed to enroll more than 20% of the analysis population in the primary cohort. In addition, the study allows for 0 to 3 roll-in patients per site, for a total maximum of 60 roll-in patients. The overall study therefore allows for up to 120 patients: 60 in the analysis population, and up to 60 additional roll-in patients.

Table 8. Safety and Performance studies for CE marking of novel devices for the treatment of mitral regurgitation.

Month, Year (CE Mark)	Study Title	Sample Size	Primary Outcome Assessment	Device/Sponsor
Sep, 2011	AMADEUS™ (CARILLON Mitral Annuloplasty Device European Union Study) Source: European Society of Cardiology	30	30 Day	Carillon / Cardiac Dimensions
Sep, 2015	Cardioband Adjustable Annuloplasty System for Transcatheter Repair of Mitral Valve Regurgitation Source: Clinical report on file at Edwards	31	30 Day	Cardioband/ Valtech, Inc.
Feb, 2016	Mitralign Percutaneous Annuloplasty First In Man Study Source: www.clinicaltrials.gov	35	30 Day	MPAS Implant/ Mitralign, Inc.

9.2 Analysis Population

- **Intent-to-treat population**

The intention-to-treat (ITT) population includes all patients in whom the study procedure has been attempted (i.e., incision).

- **Per-protocol population**

The per-protocol (PP) population includes all patients in whom the study device was introduced in the body, and do not have any major protocol deviations.

- **Roll-in population**

Up to three roll-in patients per site may be allowed, but not required (e.g., for sites with sufficient prior experience with the system). The study Sponsor will review each situation to determine when a site may start enrolling in the ITT population.

The PP population will be the primary analysis population for performance and safety assessment. The ITT population will be used for additional safety analysis. Subgroup analysis by etiology may be performed. For patients with mixed etiology, the echo core lab will determine the dominant etiology for analysis.

9.3 Statistical Analysis

A first analysis will be performed when 30 patients complete 30-day follow-up, and a second analysis when all patients in the primary cohort complete their 30-day follow-up. A pooled analysis of all patients from the primary cohort and additional cohort will also be performed. Descriptive statistics will be presented for all primary and secondary endpoints. For quantitative variables, the mean values, standard deviation, maximum and minimum will be calculated. The 95% confidence interval (CI) for the mean will be calculated when relevant.

For qualitative variables, absolute and relative frequencies are determined. Exact binomial 95% confidence interval for proportions will be calculated when relevant.

For combined and individual clinical endpoints the survival rate (and 95% CI) will be calculated using Kaplan-Meier estimator. Kaplan-Meier survival curves will also be presented when relevant.

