#### 5.1.3. Last Information Date

The last information date is defined as the latest date assessed with any available information concerning the subject (e.g., most recent date out of: baseline assessment, procedure, discharge, all follow-up visits, laboratory tests, study termination, and adverse events). Last information date is used as censor date for survival analyses.

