## 6. STATISTICAL ANALYSES

### 6.1. General Considerations

a. For continuous variables, summary statistics will include number of observations, mean, median, standard deviation, minimum, maximum, and 95% confidence intervals (based on normal distribution, unless otherwise specified) per table shells.

b. For categorical variables, summary statistics will include counts, percentages, and 95% Clopper-Pearson confidence intervals per table shells. In general, the denominator for the percentage calculation will be based on total number of subjects with evaluable data for a specified time point unless otherwise specified. Subjects with missing data will be excluded from the denominator.

c. Survival analysis techniques will be used to analyze the time-to-event variables. Summaries will include the number of subjects at risk, number of events, and number of subjects with the event. Subjects without events will be censored at their last known event-free time point. If this event-free time point occurs after the analysis time point, the days to event variable will be set equal to the analysis time point so that the subject will be included in the analysis. For subjects who did not have an event or early withdrawal and have not yet completed the analysis visit, they will be censored at their last information date. Time to first event curves will be constructed using Kaplan-Meier estimates and all post procedure results will be summarized with Kaplan-Meier estimates of event rates. Hazard ratios, confidence interval for the hazard ratios, and p-values may also be presented from a Cox proportional hazards model.

d. Descriptive statistics will be provided at each follow-up assessment, including change from baseline to subsequent time point for selected endpoints. Paired (i.e., subjects with available data at both baseline and respective time point) and unpaired data will be presented separately.

e. If insufficient data are available for summary statistics, then data will be provided only as listings.

f. Unless otherwise specified, descriptive analysis will be performed for all data. Nonparametric techniques may be used if the data does not meet the assumptions of parametric tests.

g. All analyses will be performed using SAS® Software version 9.4 or later (SAS Institute, Inc., Cary, NC).

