#### 6.4. Analyses of Secondary Endpoints

Mitral regurgitation reduction from baseline at 30 days, 6 months, 1 year and annually thereafter will be summarized with counts and percentages.

All-cause mortality rates at 30 days, 6 months, 1 year, and annually thereafter and corresponding 95% confidence intervals will be computed using the Kaplan-Meier algorithm with the standard errors being computed using Greenwood's formula.

Recurrent heart failure hospitalization at 30 days, 6 months, 1 year, and annually thereafter will be analyzed using Poisson regression.

Re-intervention rates for mitral regurgitation at 30 days, 6 months, 1 year and annually thereafter will be summarized with counts and percentages.

Composite of major adverse events (MAE) defined as cardiovascular mortality, stroke, myocardial infarction, new need for renal replacement therapy, severe bleeding and re-intervention for study device related complications at 6 months, 1 year and annually thereafter will be summarized with counts and percentages.

Change from baseline in Left Ventricular End Diastolic Volume (LVEDV), Left Ventricular End Systolic Volume (LVESV), Pulmonary Artery Systolic Pressure, 6MWT distance, BNP/NT-pro-BNP level, effective regurgitant orifice area (EROA) and mitral regurgitant volume at the protocol specified timepoints in the secondary endpoints and clinical outcomes section will be summarized by mean and standard deviation for the PP population. For the analyses of six minute walk test (6MWT), subjects unable to perform the walk due to a medical reason will be considered to have walked an actual distance of zero.

Change from baseline in Quality of Life (QoL) score, as measured by Kansas City Cardiomyopathy Questionnaire (KCCQ), and EQ5D at 30 days, 6 months and 1 year and annually thereafter will be

summarized by mean and standard deviation. Patients that are missing a baseline or follow up values will be excluded from the analysis.

Change from baseline in NYHA Functional Classification at 6 months, 1 year and annually thereafter will be presented as shift from baseline for each of the pre-specified follow-up periods. Subjects that are missing a baseline or follow-up values will be excluded from the paired analysis.

Change from baseline in tricuspid regurgitation at 6 months, 1 year and annually thereafter will be summarized with counts and percentages.

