#### 7.7. Safety Variables

Number of unique subjects who experienced adverse events will be reported by AE category for each analysis cohort.

Events will be adjudicated by the CEC according to the CEC Charter. The CEC adjudicated adverse events will be summarized by KM estimate and/or binary proportions.

Number of unique subjects who experienced heart failure rehospitalization will be reported.

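### Where non-fatal events after 30 days are reported by Kaplan-Meier, patients who die first are censored, so 1 − KM modestly overstates the proportion affected

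*Protocol*

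**What the plan says.** **General rule.** Protocol 9.3: "For combined and individual clinical endpoints the survival rate (and 95% CI) will be calculated using Kaplan-Meier estimator". SAP 6.1(c) goes further: "all post procedure results will be summarized with Kaplan-Meier estimates of event rates". For adjudicated events SAP 7.7 leaves a choice: "The CEC adjudicated adverse events will be summarized by KM estimate and/or binary proportions".

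**Censoring.** SAP 6.1(c): "Subjects without events will be censored at their last known event-free time point". SAP 5.1.3: "Last information date is used as censor date for survival analyses". That date is the latest on which anything is known about the patient, including study termination and adverse events. Death is a study exit under Protocol 7.8.7.11. Neither document mentions competing events or cumulative incidence.

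**Endpoint-specific methods.** SAP 6.3 assigns Kaplan-Meier to MAE at 30 days, and linearized rates per year of patient survival to adverse events after 30 days. SAP 6.4 assigns Kaplan-Meier to all-cause mortality but departs from it elsewhere:
- Re-intervention for MR: "Re-intervention rates for mitral regurgitation at 30 days, 6 months, 1 year and annually thereafter will be summarized with counts and percentages".
- MAE after 30 days: "re-intervention for study device related complications at 6 months, 1 year and annually thereafter will be summarized with counts and percentages".
- Heart failure admissions: "Recurrent heart failure hospitalization at 30 days, 6 months, 1 year, and annually thereafter will be analyzed using Poisson regression".

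SAP 8, which lists changes from the protocol's analyses, mentions only the implanted population.

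**The concern.** A patient who dies without a stroke can no longer have one. Kaplan-Meier treats a censored patient as still at risk and represented by those who remain, so 1 − KM estimates the risk in a setting where nobody dies first. It exceeds the proportion of treated patients who actually have the event. This applies to stroke, MI, severe bleeding, renal replacement and device-related re-intervention wherever they are reported singly by Kaplan-Meier. MAE counts cardiovascular death as an event, so there only non-cardiovascular death is censored.

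Follow-up runs to 5 years, and one stated objective is guidance for future study designs (Protocol 7.2, SAP 2.1). A late risk read as the proportion of patients affected would carry an upward bias into that planning.

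**Working it through.** The documents give no Kaplan-Meier or cumulative-incidence figure, so there is none to reproduce. The check asks how far the two estimators differ.

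**Inputs from the documents**
- Mortality of 5% per year in symptomatic severe MR (Protocol 3.3): λd = −ln(0.95) = 0.05129 per year, or 1 − 0.95^5 = 22.6% at 5 years.
- Five-year mortality of 20.8% and 26.8% in the two arms of the cited randomized trial of an earlier clip device against surgery (Protocol 3.4.3.3): λd = −ln(0.792)/5 = 0.04664 and −ln(0.732)/5 = 0.06239.
- Sample size 60, or 60 + 50 = 110 with the additional US cohort (Protocol 7.1).

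**Assumptions**
- Constant, independent hazards.
- Event hazards λe set so that 5-year 1 − KM is 5%, 10%, 20% or 30%.
- Mortality of 10%, 15% and 20% per year, for range only.

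**Formulas**
- 1 − KM(t) = 1 − exp(−λe·t)
- Cumulative incidence: CIF(t) = λe/(λe + λd) × [1 − exp(−(λe + λd)·t)]

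**Worked case** (1 − KM of 20%, mortality 5% per year)
- λe = −ln(0.8)/5 = 0.04463, and λe + λd = 0.09592.
- CIF(5) = 0.4653 × [1 − exp(−0.4796)] = 0.4653 × 0.3810 = 17.7%.
- The excess is 20.0 − 17.7 = 2.3 points, a ratio of 1.128.

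**Five-year cumulative incidence (%) when 1 − KM is:**

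| Mortality | 5% | 10% | 20% | 30% | Relative excess of 1 − KM |
|---|---|---|---|---|---|
| 20.8% at 5 years (protocol) | 4.46 | 8.94 | 17.92 | 26.94 | 11–12% |
| 5% per year (protocol) | 4.42 | 8.84 | 17.73 | 26.66 | about 13% |
| 26.8% at 5 years (protocol) | 4.30 | 8.61 | 17.28 | 26.01 | 15–16% |
| 10% per year (assumed) | 3.90 | 7.81 | 15.70 | 23.68 | 27–28% |
| 15% per year (assumed) | 3.43 | 6.89 | 13.90 | 21.03 | 43–46% |
| 20% per year (assumed) | 3.03 | 6.08 | 12.30 | 18.67 | 61–65% |

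Over the three rows that rest on the protocol's figures, the excess runs from 5 − 4.46 = 0.54 points to 30 − 26.01 = 3.99 points.

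**Shorter horizons.** In the worked case the 1-year figures are 4.36% and 4.26%. At 30 days the excess is below 0.01 point in every row.

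**Early clustering of events.** Assume 5% of patients have the event in the first 30 days and 1% per year thereafter, with 5% annual mortality. Five-year 1 − KM is 9.58% against a cumulative incidence of 9.03%. The gap is about half a point, against 1.16 points for a similar risk (10%) under constant hazards.

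**Bias against noise.** In 4,000 simulated studies of the worked case, mean 1 − KM was 20.05% (SD 5.58) at n = 60 and 19.97% (SD 4.09) at n = 110. The mean proportions affected were 17.75% and 17.69%. The bias of about 2.3 points is smaller than one standard deviation, but it does not shrink as n grows.

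**Percentages as the alternative.** SAP 6.1(b) drops subjects with missing data from the denominator and does not say whether a patient who died event-free stays in it. Take an event hazard of 0.05 and 5% annual mortality. One minus KM is 22.1%, the cumulative incidence is 19.6%, and 60.3% are alive and event-free at 5 years. If event-free deaths were dropped, the percentage would be 19.62/(19.62 + 60.26) = 24.6%, further from 19.6% than 1 − KM is.

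**The case against.** The strongest reply is that little of the plan is exposed. Endpoint-specific text names Kaplan-Meier as the sole method only for 30-day MAE, where the effect is negligible, and for all-cause mortality, where no competing death exists. Linearized rates have a denominator that ends at death. SAP 7.7 makes Kaplan-Meier optional, and the table shells, which would show which late estimates are produced, are a separate document. The study is descriptive, with no margin or test to tip. Protocol 3.4.3.3 says that, for the earlier clip device, 30-day safety outcomes resembled those at one year and clinical failures fell mainly in the first 6 months; early clustering reduces the bias. In MAE, Protocol 17 counts any death not unequivocally non-cardiovascular as cardiovascular, so few deaths would compete.

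Most of this stands, and it limits the point's reach and weight. It does not remove it. Protocol 9.3 and SAP 6.1(c) still prescribe Kaplan-Meier for individual and all post-procedure results, and SAP 7.7 permits it without limit of time. Where it is used late, the censoring rule gives a biased proportion. The specific methods in SAP 6.4 also partly conflict with that general wording, so the governing estimator is not settled in advance.

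**Conclusion.** The point holds in limited form and is minor. Where non-fatal events are reported by Kaplan-Meier beyond 30 days, 1 − KM overstates the proportion affected. At 5 years the excess is about 11–16% relative, or about 0.5–4 points for event risks of 5–30%. This rests on the protocol's mortality figures applying here, on constant independent hazards, and on assumed event risks. The primary safety result is unaffected.

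A reader might infer more than the documents support:
- *Every clinical endpoint is biased this way.* SAP 6.3 and 6.4 assign other methods to late adverse events, MAE after 30 days, re-intervention for MR and recurrent heart failure hospitalization.
- *The plan states that deaths are censored.* No sentence says so; it follows from the general censoring rule.
- *Mortality is high enough for a large bias.* Excesses of 27% and above need assumed mortality of 10% per year or more. The 50% three-year figure for FMR in Protocol 3.3 combines mortality with heart failure hospitalization.
- *One minus KM prevents comparison of FMR with DMR.* Under this model it does not depend on mortality. With an event hazard of 0.05 it is 22.1% at 5%, 10% and 15% annual mortality, while the cumulative incidence falls from 19.6% to 17.4% to 15.4%. The case for cumulative incidence is that it is the proportion affected, not that it compares better across groups.

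**What to change.** - **Protocol 9.3, SAP 6.1(c) and SAP 7.7:** keep Kaplan-Meier for all-cause mortality. For each non-fatal event beyond 30 days, estimate risk by the Aalen-Johansen cumulative incidence function with all-cause death as competing event. For cardiovascular death or MAE, if reported as time-to-event, use non-cardiovascular death as competing event. Take 95% confidence intervals from the same estimator. In SAP 7.7, replace the open choice of method with this rule.
- **SAP 6.4:** align re-intervention for MR and MAE after 30 days with the same rule. If percentages are also shown, state that patients who died event-free stay in the denominator. Poisson regression for recurrent heart failure hospitalization and the linearized rates in SAP 6.3 can stay, identified as rates and as exceptions to the general wording.
- **SAP 8:** record the change from the protocol if Protocol 9.3 is not amended.

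The cost is wording and the matching table shells. Dates of death and the cardiovascular or non-cardiovascular classification are already needed for the existing endpoints, and the SAS software named in SAP 6.1(g) can be used. No new data or patients are required.

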9.4 Missing Data

All possible steps will be taken to minimize missing data in the study, including monitoring of data forms for completeness and efforts to track and maintain contact with study patients during the follow-up period.

10 QUALITY CONTROL AND QUALITY ASSURANCE PROCEDURES

10.1 Data Safety Monitoring Board (DSMB) and Clinical Events Committee (CEC)

10.1.1 Data Safety Monitoring Board (DSMB)

The Data Safety Monitoring Board (DSMB) will be the primary independent Data and Safety advisory board for the CLASP Study. The independent DSMB will have the responsibility to assess aggregate safety data (and if requested the critical performance endpoints) on an ongoing basis, evaluate trends of adverse events and their effect on trial conduct and device risk assessment, and to recommend to the sponsor whether to continue, suspend, modify or stop the clinical investigation. The DSMB will communicate all safety-related trial recommendations to the Sponsor.

The DSMB will consist of a minimum of three physician members that are medical experts in the areas of CV surgery, interventional cardiology, and heart failure. The DSMB will also include an experienced biostatistician. Its conduct will be governed by a written DSMB charter describing its rules of operation and responsibilities.

10.1.2 Clinical Events Committee (CEC)

The Clinical Events Committee (CEC) is an independent committee that will provide a standard, systematic and unbiased assessment of pre-determined endpoints to ensure that they are adjudicated uniformly by a single group, using the definitions specified in the Protocol and CEC Charter.

The CEC will consist of a minimum of three members and will be comprised of physicians with expertise in CV surgery, interventional cardiology, heart failure, and neurology.

The scope, procedures, and events classification system will be defined in a written CEC charter.

10.2 Core Laboratory

An echocardiography core laboratory will be used for the independent assessment of image findings. Standard measurement processes will be designed by the independent core laboratory and specified in written core laboratory guidelines. Each of the selected investigative sites will receive training on the acquisition, interpretation (in especially regarding patient selection) and transmission of images. Any additional (unscheduled) imaging data should be documented and sent to Edwards.

10.3 Monitoring

All clinical sites will be monitored periodically by the Sponsor or designee to ensure compliance with the protocol and the Investigator's Agreement and that all study patients have been properly consented. The monitor will ensure that the completed eCRFs match the source documents and work with the site to resolve differences through electronically generated queries or formal action items.

10.3.1 Monitoring Methods

A study monitor will be assigned to monitor the progress of the study by the Study Sponsor. The study monitor will remain in close contact with the study center throughout the duration of the study to provide any needed materials, (e.g. study forms, etc.) answer any questions and ensure that proper staffing levels are being maintained by the Investigator. The study monitor will be responsible for verifying that patients have signed the informed consent as required by regulations, reviewing the data recorded on the eCRFs and visiting the study center periodically to observe study progress and compliance with the study protocol and regulations applicable to this clinical study.

Monitoring visits will be scheduled throughout the duration of the clinical study between the monitor and the Investigator at a mutually convenient and available time. These visits will assure the study protocol is being followed, the Institutional Review Board/Ethical Committees and Competent Authorities have been notified of approved protocol changes as required, complete records are being maintained, appropriate timely reports have been made to the Study Sponsor and the IRB/EC, device and device inventory are controlled and the Investigator is carrying out all agreed activities. Any personnel changes must be reported to the study monitor immediately and a training program scheduled and documented.

Prior to patient enrollment, an initiation visit will be completed at the study center to ensure the following:

- Institutional Review Board/Ethics Committee and applicable regulatory body approvals have been obtained and documented,
- The Investigator (s) and study personnel are appropriately trained and clearly understand the study,
- The Investigator (s) and study personnel accept the obligations incurred in undertaking this clinical study,
- The Delegation of Authority form has been completed properly.

Periodic monitoring visits will be made at the enrolling study center in accordance with center enrollment rates and / or the monitoring plan. Upon termination or conclusion of the study, the study monitor will perform a close-out visit. Additional details will be included in the Monitoring Plan.

10.4 Data Management

A qualified third party service partner will be used to host the clinical study database. The hosting facility will have a multi-level protected environment, restricted access with high-end user recognition technology, and multi-point backup of critical data. Passwords will be issued to appropriate data management personnel to ensure confidentiality and protection of the data. The Study Sponsor's data management is responsible for providing a clean data set at the end of the clinical investigation. Queries should be resolved by the Investigator or a person designated by the Investigator in a timely manner. Data snapshots will be performed for interim analysis. When all data is complete, the database will be locked and data analyzed.

